Our **primary objective** is to determine the preliminary efficacy of the intervention. **Methods:** We will conduct a **two-group cluster randomized controlled trial** (RCT). From the available 13 large Head Start centers, six centers will be randomly selected and then randomly assigned to the intervention (n=3) or control group (n=3, usual Head Start activities); 24 caregiver-preschooler dyads will be recruited from each center (N=144 dyads).

AIM 1: Determine the preliminary efficacy of *FirstStep2Health* vs control among preschoolers on proximal behavioral changes of ↑ moderate-to-vigorous PA (MVPA) measured by accelerometry (primary outcome), ↑ diet quality (e.g., ↑ fruits/vegetables, ↑ fiber, ↑ whole grains, ↑ total protein, ↑ dairy, ↓ sugar-sweetened beverages, ↓ total sugars/fats), and ↓ screen time (e.g., watching TV, playing video games); and distal anthropometric outcomes of ↓ proportion of OW/O and ↓ body mass index (BMI) z-score. We anticipate an overall decrease in BMI z-score in intervention preschoolers because we expect OW/O preschoolers’ BMI z-score to decrease and healthy-weight preschoolers to have no change. We focus on proximal behavioral changes as our primary outcome instead of distal anthropometric outcomes due to the brevity of this study and the need for behavioral changes to be maintained for at least a year before manifesting in changes in anthropometric outcomes.^{49,50} **AIM 2: Examine the preliminary efficacy of *FirstStep2Health* vs control among caregivers** on their ↑ MVPA measured by accelerometry, ↑ diet quality (e.g., ↑fruits/vegetables, ↑fiber), ↓ screen time, ↓ proportion of OW/O, ↓ BMI, ↑ knowledge, ↑ feeding practice skill, ↑ self-efficacy, ↑ parental support of their child, ↑ parenting practices, and ↑ home environment. **AIM 3: Compare *FirstStep2Health* vs control on the bidirectional relationship** (as demonstrated in the APIM) between preschoolers and caregivers on MVPA, diet quality, and screen time. Further, we will **validate established feasibility, acceptability, and satisfaction of the intervention using qualitative and quantitative data**.

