Suggestions. Fifteen randomly selected caregivers were interviewed individually. They suggested: **1)** holding each caregiver meeting on both weekday and weekend so working caregivers can attend; **2)** covering topics on alternative cooking ingredients and portion size control during the meeting; **3)** promoting more interactions via commenting on others' postings; **4)** including quick meal recipes and healthy snack ideas in the intervention cookbook; and **5)** extending the program a few more weeks. Results support the feasibility of the intervention, but preliminary efficacy needs further evaluation using a more rigorous design and larger sample size.

Fig 1. Actor-Partner Interdependence Model

C.3. CONCEPTUAL FRAMEWORK (Fig 1). The intervention is guided by an Actor-Partner Interdependence Model (APIM),⁴³ which has been used in behavioral interventions to better understand the intergenerational relationships inside a family.¹¹⁴⁻¹¹⁶ The APIM demonstrates the bidirectional relationship between preschoolers and caregivers: **1)** actor effects within preschoolers or caregivers, and **2)** partner effects between preschoolers and caregivers.⁴³ The proposed intervention targets both preschoolers' and caregivers' knowledge, skill, self-efficacy, and social support, derived from social cognitive theory,¹¹⁷ and parenting practices and home environment¹¹⁸⁻¹²³ to improve their MVPA, diet quality, and screen time, thereby reducing the proportion of OW/O and BMI. Participatory learning³⁴ will be used to improve preschoolers' knowledge, skill, self-efficacy, and social support, but will not be assessed due to preschoolers' immature cognitive development.¹²⁴ Caregivers' learning³⁴ will be improved via weekly habit-formation tasks on child feeding practices and PA and preschooler letters where preschoolers describe their desires for healthy diet and PA at home. Through simultaneously targeting both preschoolers and caregivers to maximize the actor and partner effects, the intervention is hypothesized to result in positive outcomes.

C.4. STUDY DESIGN. To decrease cross-group contamination among participants in the same location,¹²⁵ we will employ a rigorous two-group cluster RCT design by randomizing 6 centers so participants in one center are in the same group. Data will be collected at baseline (wk. 0) and immediately post-intervention (wk. 17).

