C.5. SETTING & SAMPLE. Six Head Start centers (≥ 4 classes/center) will be randomly selected from the Capital Area Community Services (CACs) Head Start and Early Childhood Programs and the Head Start for Kent County, which had 13 centers with ≥ 4 classes in 2017.^{126,127} Among the 13 centers, two had 4, one had 5, five had 6, one had 8, one had 9, two had 12, and one had 14 classes. The 13 centers cared for 1,932 preschoolers: 49% female, 20% Hispanic, 38% Black, and 39% White. Four classes will be randomly selected from each center, and 6 caregiver-preschooler dyads will be randomly selected from the eligible participants in each class (total: 6 centers, 24 classes, and 144 dyads). Inclusion and exclusion criteria are specified in **Table 1**.

C.6. SAMPLE SIZE & POWER. Due to the exploratory/developmental focus of this R21 grant proposal, our aim is to estimate effect sizes for proximal and distal outcomes in preschoolers to serve as foundation for future research. Assuming class cluster effects intraclass correlation (ICC)=0.01,^{128,129} and

significance level=.05, a sample size of 130 will provide a power of .80 to identify an effect size of 0.50, < 0.66 for MVPA achieved in the prior study after adjusting for demographics.³⁸ Given the extended intervention duration from 10 to 16 weeks and the strengthened intervention, we anticipate to also achieve an effect size of 0.50 in preschoolers' diet quality, screen time, and BMI z-score. We conservatively assume a 10% dropout.

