C.7. RECRUITMENT. The two Head Start organizations have agreed to support implementing the proposed project in their Head Start centers (**Support Letters**). Based on our prior experiences working with Head Start families, we anticipate ≥ 6 of 18 (30%) dyads per class will be willing to participate. Replacement classes will be randomly chosen if a selected class teacher refuses to participate. Building on lessons learned from prior studies and recommendations from Head Start administrators, we will involve Head Start family advocates to help with recruitment because they already have an established, trusting relationship with each family. The PI and project manager (PM) will provide participant recruitment training with communication scripts to family advocates to ensure consistency. Family advocates will distribute the recruitment packet (including cover letter, parental consent/child assent, & screening tool) in an envelope and explain the study to each caregiver in person. Each family will be asked to return the packet in a sealed envelope to the family advocate. For non-respondents, the family advocates will make a follow-up phone call, and then another packet will be mailed to each family. Each family will be asked to return the packet in an attached, prepaid envelope. Cash (\$5) will be provided for returning the packet. Prior to any data collection, written parental consent is required; if the child is age 5, written child assent is required. No data will be collected from preschoolers in the selected classes who do not have written consent or assent, but these preschoolers will be allowed to participate in intervention activities at their Head Start center. Both male and female preschoolers and caregivers will be recruited.

C.8. RANDOMIZATION AND BLINDING. Following baseline data collection, 6 randomly selected centers will be randomly assigned to intervention or control using a computerized random-number generator. Center directors and teachers will be informed of group assignment. There is no way to completely blind participants

Table 1. Inclusion and Exclusion Criteria

Preschoolers	Caregivers
Inclusion Criteria	
Parental written consent	Provide written consent
Understand and speak English	Read, understand, and speak English
3-5 years old	Primary adult caregiver (≥ 18 years old)
Enrolled in full-day or half-day Head Start program	Have at least weekly Internet access using a smartphone, tablet, or a computer

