Parental Support	Parental support scale for eating habits and physical activity ¹⁶⁷	12	3 min	$\alpha = 0.83–0.87$ ^{38,167,168}
Parenting Practices	Parenting Style and Dimensions Questionnaire ¹⁶⁹ assessing parenting styles: authoritative, authoritarian, and permissive	32	5 min	$\alpha = 0.64–0.91$ ¹⁷⁰
Home Environment	Family Nutrition and Physical Activity (FNPA) screening tool ¹⁷¹ assessing home obesogenic environments and practices	20	4 min	Correlated with child BMI ^{171,172}
Demographics	Socio-demographic questionnaire (e.g., age, sex, race)	12	3 min	N/A
Center Environment	EPAO-SR ¹⁴⁴	1-day	30 min	Related to observational data ¹⁴⁴

C.15. DATA ANALYSIS. Any missing at random (MAR) data will be imputed using procedures suggested by Potthoff.¹⁷³ For non-MAR data, a sensitivity analysis will be performed following recommended approaches for continuous and discrete outcomes.^{174–177} All analyses will use the intention-to-treat¹⁷⁸ principle. Data analysis will be disaggregated by sex in preschoolers. **AIM 1 & 2:** Mixed-effect models in SAS 9.4 will be used to evaluate the intervention efficacy. Fixed effect predictors will include group, time, groupXtime interaction, and potential confounders such as preschooler sex, race, baseline weight status, and caregiver marital status. The correlation of preschooler outcomes measured over time and dependence due to nesting in the same center or class will be accounted through center- and class-specific random cluster effect. Contrasts will quantify the intervention effects separately at the post-intervention. Holm's method will be used to statistically control for multiple comparisons.¹⁷⁹ Effect size (Cohen's d) will be calculated. **AIM 3:** Path analysis will be conducted using EQS 6.2. Model fit will be assessed using root mean square error approximation, Normed Fit Index, and Tucker Lewis index. Chi-square difference test¹⁸⁰ will be used to compare models. Model modification will be made if needed. Feasibility/acceptability/satisfaction will be determined through enrollment, intervention participation, and evaluation survey data. Recorded individual interviews will be analyzed using directed content analysis in ATLAS.ti 8 to evaluate reasons for satisfaction and suggestions for improvement.

Table 6. Method Considerations

Issue	Justification and Strategies

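### The power of .80 in C.6 rests on child-level degrees of freedom; with three centers randomized per arm, two-sided power at d = 0.50 before baseline adjustment is at most about .58

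*Combined protocol and SAP*

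**What the plan says.** **Design.** The Specific Aims, C.4 and C.8 all make the center the unit of allocation, with three centers in each arm. C.4 describes "randomizing 6 centers so participants in one center are in the same group", and C.8 says that "6 randomly selected centers will be randomly assigned to intervention or control". C.5 gives four classes per center and six dyads per class: 6 centers, 24 classes, 144 dyads.

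**Sample size (C.6).** The calculation begins "Assuming class cluster effects intraclass correlation (ICC)=0.01", takes a significance level of .05, and concludes that "a sample size of 130 will provide a power of .80 to identify an effect size of 0.50". The effect size is justified as smaller than the demographics-adjusted 0.66 for MVPA in the team's earlier study; C.2 gives that study's raw MVPA effect as d = 0.42. Dropout of 10% is assumed. C.6 gives no center-level ICC, degrees of freedom, sidedness or pre-post correlation. It also says that "our aim is to estimate effect sizes for proximal and distal outcomes in preschoolers".

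**Analysis (C.15).** Mixed models contain group, time and their interaction plus covariates, and "dependence due to nesting in the same center or class will be accounted through center- and class-specific random cluster effect". No degrees-of-freedom method is named.

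**The concern.** All four classes in a center share one arm, so the treatment comparison is made between centers. Its error can be estimated only from the variation among three centers in each arm. The loss has two parts: the center-level variance that C.6 leaves out, and the larger critical value on 4 df (2.776, against 1.979 on 128 df). The second part applies even if centers do not differ at all.

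At stake is what readers will expect of the trial. C.6 leads them to expect that a 0.50 SD effect would be detected about four times in five. It also implies an interval tight enough to help plan the larger trial that this study is meant to prepare.

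**Working it through.** **Inputs.** From C.6: N = 130 analyzed (144 × 0.9 = 129.6), d = 0.50, alpha .05, class ICC 0.01. From the Specific Aims and C.5: 3 centers per arm and 24 classes, so 130/24 = 5.42 children per class and 130/6 = 21.67 per center.

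**Assumptions.** Equal arms of 65; two-sided test unless noted; 0.50 in raw SD units; center ICCs of 0.01, 0.02 and 0.05 are illustrative, because the documents give none.

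**Formulas.** DEFF = 1 + (m − 1) × ICC; n_eff = 65/DEFF per arm; noncentrality = 0.50 × √(n_eff/2); power from the noncentral t; 95% CI half-width = t(.975) × √(2/n_eff).

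**Step 1: reproduce the plan's figure.** With class ICC 0.01, DEFF = 1 + 4.42 × 0.01 = 1.044, n_eff = 62.25 and noncentrality = 2.790. Power is .791 on 128 df and .797 by the normal approximation. With no clustering it is .808 and .813. So C.6's .80 is a child-level result, and the half-width on that basis (class ICC 0.01, 128 df) is 1.979 × √(2/62.25) = 0.355 SD.

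**Step 2: the same inputs on 4 df (critical t 2.776), before baseline adjustment.**

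| Clustering | DEFF | n_eff | Power, two-sided | Power, one-sided | Half-width (SD) | Smallest d at .80, two-sided |
|---|---|---|---|---|---|---|
| None | 1.000 | 65.00 | .578 | .755 | 0.487 | 0.660 |
| Class ICC 0.01 | 1.044 | 62.25 | .561 | .740 | 0.498 | 0.674 |
| Center ICC 0.01 | 1.207 | 53.87 | .505 | .687 | 0.535 | 0.725 |
| Center ICC 0.02 | 1.413 | 45.99 | .448 | .630 | 0.579 | 0.784 |
| Center ICC 0.05 | 2.033 | 31.97 | .336 | .504 | 0.694 | 0.941 |

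The first row is a ceiling at N = 130, because it assumes no clustering. Simulated t tests on six center means (400,000 replicates) gave .578, .560, .504, .447 and .335 for the five two-sided rows. If all 144 children were analyzed, the two-sided ceiling would be .619.

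**Step 3: what baseline data could recover.** The pre-post correlation r is assumed and 4 df are kept. With baseline as a covariate, variance is multiplied by 1 − r²; as a group-by-time change contrast, by 2(1 − r). The change rows apply the same design effect to change scores, which is a further assumption. All power figures are two-sided.

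| Clustering | Covariate, r = .5 / .7 | r needed for .80 (covariate) | Change, r = .5 / .7 |
|---|---|---|---|
| None | .695 / .842 | .652 | .578 / .784 |
| Class ICC 0.01 | .678 / .827 | .671 | .561 / .767 |
| Center ICC 0.01 | .618 / .774 | .724 | .505 / .710 |

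Covariate-adjusted half-widths at r = .5 / .7 are 0.422 / 0.348 SD with no clustering, 0.431 / 0.355 with class ICC 0.01, and 0.463 / 0.382 with center ICC 0.01.

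**The case against.** - **This is an exploratory R21 whose aim is estimation.** That is fair, and it softens the consequence of a non-significant result. But C.6 still asserts a power, C.15 plans tests with Holm's correction, and for estimation the interval width is what counts.
- **The headline figures are unadjusted, whereas C.15 plans a repeated-measures model with covariates.** This is the strongest point. At r = .7 with baseline as covariate, .80 is passed on 4 df for zero or class-only clustering, and with class ICC 0.01 the half-width returns to 0.355 SD. However, C.6 neither claims this gain nor gives a correlation. C.15 specifies group, time and their interaction, not the baseline outcome as a covariate; read as a change contrast, r = .5 recovers nothing.
- **The test may be one-sided.** Sidedness is not stated, and the aims are written directionally. Unadjusted, one-sided power still stops at .755. With baseline as covariate, a one-sided test would reach .80 at r of about .35 (no clustering), .40 (class ICC 0.01) or .52 (center ICC 0.01). The correlation needed therefore depends on a choice that C.6 leaves open.
- **The .80 may have been reached another way.** A one-sided test with the 0.01 applied at center level and 18 or 22 class-level df also gives .80 or .81. That is a less natural reading of C.6, and it too ignores the 4 center df.
- **The center random effect already handles clustering.** It handles the variance component. It does not fix the reference distribution: with three centers per arm that variance is poorly estimated, and a fit that sets it to zero could test on many more df.

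**Conclusion.** The concern holds. C.6's arithmetic is sound for its own unit of inference, but that is not the unit randomized. For 130 children, d = 0.50 and a two-sided .05 test before baseline adjustment, power is .58 at most, about .50 at an assumed center ICC of 0.01 and .34 at 0.05. An observed d of 0.50 at center ICC 0.01 would carry an interval of 0.50 ± 0.535, that is −0.035 to 1.035.

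The margin that C.6 draws from choosing an effect "to identify an effect size of 0.50, < 0.66 for MVPA achieved in the prior study after adjusting for demographics" also disappears: 0.66 is the smallest effect detectable with .80 power on 4 df even with no clustering.

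The ceiling needs no assumed ICC. The lower figures depend on the center ICC chosen, and all of them treat 0.50 as raw SD units. Power of .80 is not out of reach, but it depends on a pre-post correlation that C.6 does not state. This should be fixed; it does not undermine the design.

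**What to change.** Keep N, the centers and the outcomes.

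**C.6.** Restate power and precision on the center basis, and list sidedness, the 4 df, a range of center ICCs, the scale of d, and any pre-post correlation relied on, with its source. If the test is two-sided, wording could be:

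> With 6 centers (3 per arm), 130 preschoolers and a two-sided .05 test on 4 df, before baseline adjustment the expected 95% CI half-width is 0.487 SD (zero ICC) to 0.535 SD (center ICC 0.01). Power for d = 0.50 is about .58 to .50 (.34 at center ICC 0.05), and the smallest d detectable with power .80 is 0.660 to 0.725.

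If baseline adjustment is intended, add the matching adjusted figures, so that C.6 describes the model that C.15 will fit.

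**C.15.** Add one sentence: the group contrast and its confidence interval use center-level degrees of freedom (4), including when the center variance is estimated as zero.

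**Cost.** One recalculation, some rewording in C.6 and one sentence in C.15. The drawback is a lower stated power unless a supported correlation is supplied.

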C. APPROACH To ensure **rigor**, the study will use a rigorous design, reliable and valid instruments, and training and supervision to maintain ethical conduct and intervention integrity.

C.1. RESEARCH TEAM. Our multidisciplinary team includes researchers from nursing, nutrition, child development, engineering, and biostatistics. The team includes experts in preschooler obesity prevention (PI [name], Co-I [name], & Consultant [name]),^{4,38,106} Internet/social network-based intervention (PI [name] & Co-I [name]),^{38,107,108} mHealth (Co-I [name]),¹⁰⁹⁻¹¹¹ and cluster RCTs (Co-Is [name] & [name]).^{112,113}

C.2. PRELIMINARY STUDIES. In preparation for this application, we completed two systematic reviews^{16,33} and two preliminary studies.^{4,38,67,87} The systematic reviews^{16,33} suggest that OW/O interventions should target preschoolers via participatory learning³⁴ and provide caregivers with parenting skill training and behavioral change strategies. One preliminary study,⁴ with 32 Head Start caregivers, identified the unique needs and barriers to healthy behaviors in Head Start families and supported the intervention strategy of involving caregivers through an online support group supplemented with face-to-face meetings. The PI collaborated with the established research team on a quasi-experimental study to examine the feasibility and preliminary efficacy of the 10-week *FirstStep2Health* intervention.^{38,67,87} Sixty-nine dyads participated (39 in intervention). About 81% of caregivers and 46% of preschoolers were OW/O, and 92% reported no difficulty to get the foods they needed.³ **Feasibility.** Enrollment rate was 37% and retention rate was 99%. Preschooler participation was 77%, and caregiver participation was 87%. Completion rates for weekly tasks and quizzes were 82% and 88%, respectively. About 94% of caregivers were satisfied with the program; 97% would recommend the program to others. **Efficacy.** Intervention increased MVPA (raw $d=0.42$) and fruit/vegetable intake ($d=0.40$), and decreased screen time ($d=-0.21$) and BMI z-score ($d=-0.30$) in intervention preschoolers. It also increased caregivers' fruit/vegetable intake ($d=0.40$), but had a small effect on their MVPA ($d=0.08$) and BMI ($d=-0.07$).

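### C.6 expects d = 0.50 for screen time, BMI z-score and diet quality with no figure behind it, and its .80 power counts class clustering but not the six randomized centers

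*Combined protocol and SAP*

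**What the plan says.** C.6 (Sample Size & Power) describes the purpose as exploratory: "our aim is to estimate effect sizes for proximal and distal outcomes in preschoolers to serve as foundation for future research". Its calculation starts from "Assuming class cluster effects intraclass correlation (ICC)=0.01" and a significance level of .05. It states that 130 dyads give a power of .80 at an effect size of 0.50, and notes that this is below the adjusted MVPA effect of 0.66 from the prior study. It then turns to three further outcomes in the children: BMI z-score, screen time and diet quality. The expectation for them is worded "we anticipate to also achieve an effect size of 0.50 in", and the only reason offered is "Given the extended intervention duration from 10 to 16 weeks and the strengthened intervention". Dropout is taken as 10%.

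C.2 (Preliminary Studies) gives the results of the 10-week, quasi-experimental prior study of 69 dyads. For two of these outcomes it reports "and decreased screen time ($d=-0.21$) and BMI z-score ($d=-0.30$) in intervention preschoolers". For physical activity and diet it reports "Intervention increased MVPA (raw $d=0.42$) and fruit/vegetable intake ($d=0.40"). Only the MVPA value is labelled raw. A.1 reports BMI effects of d = 0.19 in earlier preschool interventions, and 0.10 where at least half the children were of low SES.

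The Specific Aims (Aim 1) anticipate a decrease in BMI z-score, with no size. They justify behavioral primary outcomes partly by "the need for behavioral changes to be maintained for at least a year before manifesting in changes in anthropometric outcomes". On timing, C.4 states: "Data will be collected at baseline (wk. 0) and immediately post-intervention (wk. 17"). C.4 and C.8 randomize six centers, three per arm, and C.15 plans a mixed model with random effects for both center and class.

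**The concern.** There are two separate questions. The first is whether anything in the protocol supports 0.50 for outcomes whose only prior estimates are 0.21, 0.30 and 0.40. For MVPA, C.6 plans below its prior adjusted value. For these outcomes it plans above the prior values, and the word linking them to MVPA invites the reader to carry the .80 power across.

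The second is whether .80 is the right figure at 0.50, for any outcome. The design effect counts classes, while the unit of randomization is the center and the planned model allows for center variation.

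What is at stake is how the results are read. The estimates are meant to inform a later trial. A reader who takes C.6 at its word would expect about half an SD, and four-in-five power to detect it, for all four outcomes.

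**Working it through.** **Inputs.** From C.5 and C.6: 130 analysed, so 65 per arm; 24 classes; class ICC 0.01; alpha .05. From C.4: 6 centers, 3 per arm. Assumptions: two-sided test, equal cluster sizes, no baseline adjustment, no Holm correction.

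**Reproducing C.6.** Dyads per class m = 130/24 = 5.42. Design effect = 1 + (5.42 − 1) × 0.01 = 1.044. Unclustered n per arm = 2 × (1.96 + 0.84)²/0.50² = 62.8, so N = 2 × 62.8 × 1.044 = 131. The stated 130 reproduces, and 144 × 0.9 = 129.6 agrees with the dropout allowance. The .80 is therefore a two-sided calculation that allows for class clustering only.

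**Power by effect size.** SE(d) = √(2 × 1.044/65) = 0.179. Power comes from the noncentral t with noncentrality d/SE. The test of a center-randomized effect has 6 − 2 = 4 degrees of freedom; the class-level figure uses 130 − 2 = 128.

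| Basis | d = 0.50 | 0.40 | 0.30 | 0.21 |
|---|---|---|---|---|
| Class-level, 128 df | .79 | .60 | .38 | .21 |
| Center-level, 4 df, no added center variance | .56 | .40 | .25 | .15 |
| 4 df, center ICC 0.01 (assumed) | .49–.51 | .35–.36 | .22–.23 | .13–.14 |

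The range in the last row depends on whether the class ICC of 0.01 already contains the center part (design effect 1.207) or the center ICC is added to it (1.251).

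The 95% CI half-width with 4 df is 2.776 × 0.179 = 0.50 SD, or 0.53 to 0.55 SD with center ICC 0.01. The effect detectable with .80 power is about 0.51 at class level and 0.67 with 4 df.

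**Baseline data.** C.15 models both time points, so the table is not the power of the planned analysis. The documents give no baseline correlation ρ. The variance factor is 1 − ρ² for an ANCOVA-type estimator and 2(1 − ρ) for a group-by-time change contrast. With 4 df and no added center variance:

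| ρ (assumed) | d = 0.50 | d = 0.30 | d = 0.21 |
|---|---|---|---|
| 0.5 | .68 / .56 | .32 / .25 | .18 / .15 |
| 0.8 | .93 / .90 | .56 / .52 | .32 / .30 |
| 0.9 | >.99 / .99 | .82 / .80 | .53 / .51 |

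Each cell shows ANCOVA-type / change contrast.

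**Support for 0.50.** The ratios to the prior values are 0.50/0.21 = 2.4, 0.50/0.30 = 1.7 and 0.50/0.40 = 1.25. Two generous rescalings, neither made in the documents:
- By duration, 16/10 = 1.6: screen time 0.34, BMI z-score 0.48.
- By the raw-to-adjusted ratio for MVPA, 0.66/0.42 = 1.57: screen time 0.33, BMI z-score 0.47.

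Screen time stays well short under both. BMI z-score comes close, but A.1's 0.19 and 0.10 for BMI point the other way: 0.50 is 2.6 and 5 times those values.

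**What the prior study excludes.** If its values are between-group (39 vs 30, no clustering; assumptions), SE = √(1/39 + 1/30 + d²/138) = 0.244. The 95% intervals are −0.18 to 0.78 for 0.30 and −0.27 to 0.69 for 0.21. Both contain 0.50.

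**The case against.** The tempting stronger reading is that C.2 contradicts C.6. It does not. C.2 reports estimates from a small 10-week study; C.6 states an expectation for a longer programme. The strengthening has content too: C.10.1 adopts caregiver requests such as weekday and weekend meetings and portion-size material. An expectation above an imprecise estimate is optimism, and for BMI z-score duration scaling alone nearly closes the gap. That stands, and it leaves the point as lack of support. It does not help screen time.

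A reader might also infer that C.6 creates the conflict with the one-year remark. In fact the Specific Aims themselves both anticipate a BMI z-score decrease and say anthropometric change needs at least a year, and C.2 reports a BMI z-score effect after 10 weeks. The remark explains the choice of primary outcome. C.6 sharpens a tension already there by attaching a size to week 17.

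A third inference would be that the trial lacks .80 power in its planned analysis. The documents do not support that either. With a high baseline correlation, power at 0.50 exceeds .80 even with 4 df. Nothing in C.6 claims such a correlation, so its .80 cannot rest on one.

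Finally, the aim is exploratory, N rests on MVPA, and no progression rule uses 0.50. All of this is correct and limits the consequence. It does not make the stated figures right.

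**Conclusion.** The point holds as an unsupported assumption together with a power figure that the design does not deliver on C.6's own inputs. The 0.50 has no figure behind it for any of the three outcomes; the gap is clearest for screen time, weaker for BMI z-score, and smallest for diet quality, where the only prior value is for one component.

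The .80 at 0.50 falls to about .56 once the six randomized centers set the degrees of freedom, and to about .50 if center ICC is 0.01. At the prior values power is .40 or less on the same basis. These figures assume a two-sided test and no baseline adjustment; the size of any recovery depends on a baseline correlation and an estimator that the plan does not state. Sample size, primary outcome and analysis are not called into question by this point.

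**What to change.** In C.6:

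1. Limit the power statement to MVPA at d = 0.50. Restate it with center-level degrees of freedom, and give the center ICC, any baseline correlation assumed, and the estimator C.15 will use (ANCOVA-type or change contrast).
2. Remove the 0.50 expectation for screen time, BMI z-score and diet quality. Give the prior values 0.21, 0.30 and 0.40 (fruit/vegetable intake), say whether each is raw or adjusted, and state that these outcomes are for estimation. The duration rationale may stay without a number.
3. If power is quoted for these outcomes, give it as a range over stated baseline correlations. A flat statement based on an unadjusted comparison would describe an analysis that C.15 does not plan.

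Reconcile the one-year remark in the Specific Aims with the BMI z-score decrease anticipated there and with whatever C.6 then says about week 17.

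The cost is a few sentences in C.6 and one in the Specific Aims, and less favourable stated expectations. Participants, primary outcome and model stay as they are; the estimator only has to be named.
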